Our research team is currently conducting experiments in sheep, but the data have not been published. In these studies, 3 sheep have been anesthetized and placed on cardiopulmonary bypass. Between 5-7mLs of 1:1000 diluted Fluorescite® was applied to the epicardium and endocardium, and images were obtained using the Cellvizio Imaging system. After the images were obtained, the animals were taken off bypass. ECGs were obtained at baseline, after re-perfusing the hearts, and after the animals were taken off bypass. The ECGs confirmed that after the procedure, the hearts resumed normal baseline cardiac activity. Visual examination of the hearts also confirmed normal ventricular function and vigorous activity. Furthermore, preliminary imaging data from these studies confirms that we are able to discriminate conduction tissue from the images taken.

D. Design and Methods

(1) Study Design

We propose a descriptive pilot study to assess the safety and feasibility of using fiber-optic confocal microscopy during cardiac surgery to image the endocardium and epicardium. 6 patients undergoing surgery for closure of atrial septal defect will be enrolled in this study.

All enrolled subjects will receive standard of care for cardiac surgery and the operation will be conducted according to routine procedure. After the sternotomy, the subject will be placed on cardiopulmonary bypass. After cardioplegic infusion and cardiac arrest, the right atrium will be opened to visualize the atrial septal defect.

At this juncture, fluorescein sodium at a concentration of 100ug/ml in sterile saline will be applied topically to the myocardium, where it will diffuse into the endocardium and epicardium. A total volume of 5ml will be applied. The surgeon will confirm there are no visual indicators of an allergic reaction to the fluorescein study drug. As long as there is no appearance of tissue damage, the imaging will proceed. If any signs of allergy or intolerance occur, the dye will be immediately flushed out and no images will be obtained.

The imaging probe of the Cellvizio system will then be applied in direct contact to the region of interest with minimal pressure for approximately 90 seconds. During this period, Cellvizio Software and Viewer will be used to obtain images. The total additional time on bypass will be approximately 3 minutes.

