Once the imaging procedure has been completed, the heart surface will be washed with saline and evacuated using a suction apparatus, to ensure all fluorescein has been removed and will

not enter the circulatory system. After that, the remainder of the operation will proceed in the usual fashion. As per standard of care for patients undergoing cardiac surgery, an intraoperative echocardiogram will be performed after the subject is separated from bypass.

The expected hospitalization for the Atrial Septal Defect (ASD) is 3-5 days post-operation. It is not expected that participation in this study will increase the post-operative hospital stay or post-hospitalization recovery. The principal investigator (PI) and research team will monitor clinical labs, electrocardiograms (EKGs), and echocardiograms for any evidence of adverse events. No additional follow-up testing, outside of standard clinical monitoring, are planned. In accordance with standard of care, all subjects will receive a pre-discharge EKG and trans-thoracic echocardiogram.

Image files will be exported out from the Cellvizio system, de-identified, and provided to the blinded raters. The image files will be assessed for quality and the ability to discriminate tissue types.

(2) Patient Selection and Inclusion/Exclusion Criteria

Patients undergoing cardiac surgery for ASD repair at Boston Children's Hospital will be enrolled in this study. Surgery for ASD repair exposes the conduction system of the heart, allowing access to the AWM and nodal tissue for image capture by the Cellvizio system. Congenital heart defects such as ASD are most often diagnosed and repaired in infants and children, which is why conducting this study in a pediatric population is appropriate. Additionally, the FCM has a pre-defined field of focus, with a depth ranging from 55 to 65 μm . Therefore, this technology is more suited to pediatric hearts, as adult hearts are thicker and the conductive tissue may be too deep to be identified using this method.

Inclusion criteria:

- Males and females between 30 days and 21 years old
- Undergoing elective surgery for closure of isolated secundum atrial septal defect
- Both parents attend pre-operative clinic appointment, to provide 2 parent consent, or an adult participant (age 18-21) may provide consent for him/herself

Exclusion criteria:

- Prior history of adverse reaction to fluorescein sodium
- Prior history of renal failure or abnormal renal function

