With several patients eligible weekly, it should be feasible to complete subject recruitment, enrollment, and follow-up within 6 months after study activation. Lead time will be needed to secure FDA and BCH Institutional Review Board (IRB) approval.

E. Adverse Event Criteria and Reporting Procedures

(1) Specification of Safety Parameters

Comprehensive assessments of any apparent toxicity experienced by the study subject will be performed throughout the course of the study. All safety events experienced by study subjects for the duration of the study will be documented. The types of adverse events that must be reported and procedures for appropriately recording, grading and reporting are outlined in this section.

(2) Definition of an Adverse Event (AE) or Medical Event

According to FDA regulations, an adverse event (AE) is any undesirable, noxious, or pathological change compared to preexisting conditions occurring to or in a study subject enrolled in a clinical trial, whether or not the event is considered related to the test drug. This includes the time periods during which no medication is administered to a study subject, such as run-in or follow-up periods. An adverse event is further defined as any change in structure (signs) or function (symptoms) of the body that occurs while the study subject is receiving study drug/placebo. AEs include the following types of changes:

- Suspected adverse drug reactions, which are any adverse events for which there is a reasonable possibility that the drug caused the adverse event. A reasonable possibility implies that there is evidence that the drug caused the event.
- Other medical experiences regardless of their relationship to the test drug, such as injury, surgery, accidents, extensions of symptoms or apparently unrelated illnesses, and significant abnormalities in clinical laboratory values, physiological testing, or physical examination findings.

(3) Definition of Serious Events (Serious Adverse Events, Serious Suspected Adverse Reactions or Serious Adverse Reactions)

A serious adverse event including a serious suspected adverse reaction or serious adverse reaction as determined by the Investigator or the sponsor is any event that results in any of the following outcomes:

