- Possibly Related – There is a reasonable possibility that the study product caused the adverse event. Reasonable possibility means that there is evidence to suggest a causal relationship between the study product and the adverse event.

Specific adverse events considered related or possibly related to study participation have been identified as: myocarditis or ventricular dysfunction, as measured by ejection fraction and fractional shortening. These will be reported to the FDA in an IND Safety Report, per discussion with the FDA.

Specific ECG and rhythm abnormalities requiring DSMB review prior to enrollment of next patient:

1. AV block > the a PR interval > 220 msec lasting more than 2 hours post completion of cardiopulmonary bypass. This does not include transient Wenkebach with sleep/rest/hypothermia.
2. Need for atrial pacing or junctional rhythm lasting more than 6 hours post completion
3. Hypotension or ventricular dysfunction requiring pressor support > 5mcg/kg/min of dopamine more than 4 hours post completion of cardiopulmonary bypass.

- Not Related – There is not a reasonable possibility that the administration of the study product caused the event, and/or there is a more plausible explanation for the adverse event than administration of the study product.

(7) Recording and Reporting Procedures

Reporting Adverse Events and Serious Adverse Events

All AEs will be followed until the time the event is resolved or medically stable, or until subject is discharged from hospital, whichever comes first. AEs may be discovered through any of these methods:

- Observing the subject
- Questioning the subject, which should be done in an objective manner
- Receiving an unsolicited complaint from the subject
- Review of medical records/source documents

All AEs must be recorded accurately on the Adverse Event log for each study subject. The date of onset and duration of the AE, grade, whether it was expected or unexpected, action taken, date of resolution (if applicable) and outcome of the event must be recorded. The investigator will treat subjects experiencing adverse events appropriately and observe them at suitable intervals until their symptoms resolve or their status stabilizes or they are discharged from the hospital.

SAEs and unexpected problems will be reported promptly to BCH IRB according to local regulations and guidelines.

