FCM image files obtained for the study will be stored on a password-protected hard drive connected to the Cellvizio system. The image files will be exported, labeled only with the subject's study ID number, and provided to the blinded raters for analysis.

G. Quality Control Method

All study related tasks will follow Good Clinical Practice guidelines. A manual of operations (MOO) will be developed to detail the specific procedures to be conducted and data to be collected. Any significant deviations or exceptions to the protocol will be reported to the IRB and FDA in addition to being discussed among the investigators, and the PI will develop and implement a plan of action as needed (e.g. modification to MOO, study amendment, etc.). The PI will ensure the retention of all necessary records and reports for a minimum of 2 years after the discontinuation of the IND. The FDA will be allowed access to these records. A record of accountability of all investigational drug dispositions will be maintained, including batch and lot numbers and storage records.

H. Data Monitoring

Monitoring and auditing procedures as outlined in the Monitoring Plan will be followed to ensure that the entire study is conducted, documented, and reported in accordance with the IRB approved protocol, the International Conference on Harmonization (ICH) Good Clinical Practice (GCP) Guidelines, and applicable regulatory requirements of Boston Children's Hospital.

Monitors will review and verify protocol compliance with particular focus on AE/SAE reporting, CRF data, source documentation, informed consents, and any other study-related documentation, including review of hospital pharmacy procedures, drug accountability documentation, and drug storage facilities and records.

I. Data Analysis Plan

The FCM image files will be provided post-surgery to blinded raters, who will attempt to categorize the image files as either myocardium or nodal tissue. The raters will note if the image quality is not high enough to discriminate tissue types.

J. Statistical Power and Sample Considerations

This is a single site, descriptive, pilot study, so no power calculations have been performed. Six subjects will provide enough images to determine the feasibility of a larger randomized trial, to be performed in the future.

K. Study Organization

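### The between-subject safety hold acts on enrolment and on findings within hours of bypass, so the next subject can be exposed before the previous subject's pre-discharge EKG and echocardiogram are seen

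*Protocol*

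**What the plan says.** Four parts of the protocol bear on this.

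- **Number and pace.** Section D(1): "6 patients undergoing surgery for closure of atrial septal defect will be enrolled in this study". Section D(6): "With several patients eligible weekly, it should be feasible to complete subject recruitment, enrollment, and follow-up within 6 months after study activation".
- **Safety tests.** Under D(1), "an intraoperative echocardiogram will be performed after the subject is separated from bypass", and later "all subjects will receive a pre-discharge EKG and trans-thoracic echocardiogram". On timing, "The expected hospitalization for the Atrial Septal Defect (ASD) is 3-5 days post-operation". No further follow-up testing is planned, and under E(7) adverse events are followed no later than discharge.
- **Harms of interest.** Section E(6): "Specific adverse events considered related or possibly related to study participation have been identified as: myocarditis or ventricular dysfunction", the latter measured by ejection fraction and fractional shortening (EF/FS). These go to the FDA in an IND Safety Report.
- **The hold.** E(6) then gives a list introduced as "Specific ECG and rhythm abnormalities requiring DSMB review prior to enrollment of next patient". It has three entries: AV block or a prolonged PR interval persisting beyond 2 hours; atrial pacing or junctional rhythm beyond 6 hours; and hypotension or ventricular dysfunction still needing pressor support above a stated level beyond 4 hours. The times run from the end of bypass (the second entry does not finish the phrase, but I read it the same way).

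Section D(2) ties two-parent consent to the pre-operative clinic appointment. E(7) has the DSMB chair told of all serious adverse events, without a deadline or an automatic hold.

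**The concern.** Safety is the primary aim, and the animal work described in section C is in rats and three sheep. In a series of six, the main benefit of patient-by-patient review is that what is learned from one subject reaches the decision to expose the next. That requires the hold to cover the harms of interest, to come after the test that would show them, and to act on the exposure itself.

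The E(6) hold falls short on each count for one class of event. Myocarditis is not on the list. Ventricular dysfunction is on it only when it needs the stated pressor support. The last scheduled test that could show either is the pre-discharge echocardiogram, and no section asks for its result before the next subject receives dye and probe. The hold also stops enrolment, and a subject who consented in clinic may already be enrolled when the event appears.

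**Working it through.** The plan has no figure of its own to reproduce: section J states "This is a single site, descriptive, pilot study, so no power calculations have been performed". The check sets the timings side by side and then asks how often they would collide.

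**1. When each safeguard can act**

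| Safeguard | Earliest time | Acts on |
|---|---|---|
| Post-bypass echocardiogram, D(1) | same day | nothing stated |
| E(6) hold | more than 2, 4 or 6 hours after bypass | enrolment of the next subject |
| Notice of SAEs to DSMB chair, E(7) | once the SAE is recognised | nothing automatic |
| Pre-discharge EKG and echocardiogram, D(1) | by about day 3-5 | nothing stated |

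The hold's triggers mature early in the stay: 2 h / 120 h = 1.7% of a 5-day stay at the least, and 6 h / 72 h = 8.3% of a 3-day stay at the most. They would normally be known before a next-day case, but not necessarily before a second case on the same day. The pre-discharge tests come at the other end of the stay.

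**2. How often the next exposure would come first**

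Inputs: stay L = 3 to 5 days (D(1)), used as a stand-in for when the pre-discharge tests are read; five gaps between six subjects; exposure rate r per week, which the protocol does not give. Section D(6) speaks of several eligible patients per week, but eligible is not exposed, so r is varied.

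Assuming Poisson arrivals:

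- P(next exposure within L days) = 1 − exp(−rL/7)
- P(at least one overlap in five gaps) = 1 − exp(−5rL/7)

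| r per week | Mean gap 7/r | Per gap, L = 3 to 5 | At least one in five gaps |
|---|---|---|---|
| 0.25 (six in 24 weeks) | 28 days | 10% to 16% | 41% to 59% |
| 1 | 7 days | 35% to 51% | 88% to 97% |
| 2 | 3.5 days | 58% to 76% | 98.6% to 99.9% |

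Worked example: r = 2, L = 3 gives 1 − exp(−6/7) = 0.576.

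**3. Sensitivity to the arrival assumption**

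If exposures were evenly spaced, overlap would need 7/r < L, that is r above 7/5 = 1.4 per week for a 5-day stay or 7/3 = 2.3 per week for a 3-day stay. Six exposures spread evenly over about 182 days are some 30 days apart (182/6), with no overlap. The result therefore depends on both rate and clustering, neither of which the protocol fixes.

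**4. Cost of waiting**

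Five gaps × 3 to 5 days = 15 to 25 days. Against about 183 days that is 15/183 = 8% to 25/183 = 14%.

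**The case against.** The strongest reply is that the protocol already works patient by patient. The E(6) wording presupposes it. The listed triggers cover the main rhythm and haemodynamic harms, an echocardiogram is done the same day, the team reviews records during the stay, and SAEs go to the DSMB chair. That stands. A reader might infer that nothing at all spaces the six exposures, or that a signal in one subject cannot protect the next. The documents do not support either: for early harm, the existing hold and the same-day echocardiogram largely do the job.

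Second, the D(6) sentence is about feasibility. It does not plan overlapping exposures, and it counts eligible patients. An assumed 2 to 5 eligible per week gives 2 × 3/7 = 0.86 to 5 × 5/7 = 3.57 per stay, but it would be wrong to read these as exposed subjects: consent and the exclusions come in between. This also stands. The sentence shows only that the protocol allows a pace faster than one per stay.

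Third, section K has one person do all dye administration and imaging. That rules out simultaneous cases, but not consecutive ones on the same or the next day.

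Fourth, the agent is FDA-approved for intravenous use, is applied here topically at 1:1000 dilution, and is washed off afterwards. This lowers the expected risk. It does not remove the protocol's own decision to name myocarditis and ventricular dysfunction as study-related.

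Finally, the manual of operations mentioned in section G might set the sequence. It is not shown. A rule that limits exposure belongs with the hold in the protocol, and the hold as written there points to enrolment.

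**Conclusion.** The point holds for a limited class of harm: myocarditis, or EF/FS dysfunction not needing the stated pressor support, first seen on the pre-discharge tests. For these, the protocol as written lets a further subject be exposed before the finding exists, whether that subject is already enrolled, is operated on the same day, or comes to surgery within the previous subject's stay. Even a listed early trigger may mature too late for a second case on the same day, and does not clearly hold a subject already enrolled.

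The chance of overlap per gap runs from about 10-16% at 0.25 exposures per week to 58-76% at 2 per week. These figures rest on assumed rates, on Poisson arrivals and on the pre-discharge tests being read at the end of a 3-5 day stay. Earlier tests or evenly spaced surgery would lower them. They give the chance of overlapping exposure, not of harm. I also assume that enrolment takes place at or soon after consent, which the protocol does not define.

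This is an inexpensive improvement to the primary aim and should be made. It does not show that the trial lacks safety oversight.

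**What to change.** Reconcile D(1), D(6) and E(6) so that they say together what must be known about one subject before the next is exposed:

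- state that subjects are exposed sequentially;
- tie the between-subject check to the next subject's exposure rather than to enrolment;
- have the check take account of the pre-discharge EKG and echocardiogram already planned, and of the events that E(6) itself names as related or possibly related.

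The clinical criteria for proceeding or holding are for the sponsor and the DSMB to set; none is proposed here.

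The change takes a few sentences and adds no tests or staff. Its price is roughly 15-25 days of calendar time in total at the expected stay, within the planned 6 months. It is not a ceiling, since 3-5 days is an expected stay and a prolonged one would lengthen that gap. Some eligible patients whose surgery falls inside a waiting period would not be imaged.

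### The between-subject hold rests on events read 2 to 6 hours after bypass, so the next subject can be exposed before the pre-discharge echocardiogram that may first show late myocarditis or ventricular dysfunction

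*Protocol*

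**What the plan says.** **Size and pace.** Protocol D(1): "6 patients undergoing surgery for closure of atrial septal defect will be enrolled in this study". D(6): "With several patients eligible weekly, it should be feasible to complete subject recruitment, enrollment, and follow-up within 6 months after study activation". No section gives an expected exposure rate or a minimum interval between subjects.

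**Planned tests.** D(1) has two echocardiograms. The first is on the day of surgery: "an intraoperative echocardiogram will be performed after the subject is separated from bypass". The second comes at the end of the stay: "all subjects will receive a pre-discharge EKG and trans-thoracic echocardiogram". No day is fixed for the second, but D(1) also says "The expected hospitalization for the Atrial Septal Defect (ASD) is 3-5 days post-operation", which puts it at about day 3-5.

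**Events singled out.** E(6) names "myocarditis or ventricular dysfunction, as measured by ejection fraction and fractional shortening" as related or possibly related to participation and reportable to the FDA in an IND Safety Report.

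**Hold rule.** E(6) then lists "Specific ECG and rhythm abnormalities requiring DSMB review prior to enrollment of next patient". The three items are:
- AV block or PR prolongation "lasting more than 2 hours post completion of cardiopulmonary bypass";
- atrial pacing or junctional rhythm beyond 6 hours;
- hypotension or ventricular dysfunction that still needs a stated level of pressor support beyond 4 hours.

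**Other reporting.** E(7) has all SAEs notified to the DSMB chair, with the investigator and the DSMB panel recommending any further action.

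**The concern.** The hold acts on what can be seen within hours. Two of the outcomes that the protocol itself ties to participation may not be seen by then: myocarditis, and ventricular dysfunction that does not reach the pressor criterion. If they develop after the operating room, the next planned echocardiogram is the pre-discharge one. Nothing asks for it to be read before the next subject receives dye and probe contact, and an abnormal result on it is not among the listed triggers.

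The hold is also placed on enrollment. Under D(2), consent is given at the pre-operative clinic, so a subject who has already consented and is awaiting surgery is not clearly covered when a trigger occurs in someone else.

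Safety is the primary aim and there are only six subjects. Each exposure made before a late finding is known is a sixth of the sample, and the DSMB cannot act on a result that does not yet exist.

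**Working it through.** The protocol gives no figure to reproduce here; section J states that no power calculation was done. The check compares the gap between subjects with the time at which each kind of safety information becomes available.

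**Inputs from the protocol**
- 6 subjects, hence 5 gaps (D(1)).
- 6 months, taken as 26 weeks (D(6)).
- Pre-discharge tests at day 3-5, inferred from the stay (D(1)).
- Hold windows of 2, 4 and 6 hours (E(6)).

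**Assumptions**
- Exposures arrive at random (Poisson).
- The wait for the pre-discharge tests is 5 days, with 3 days as the lower end.
- The exposure rate is unknown. Slowest pace that meets the timeline: 6/26 = 0.23 per week. Illustrative faster paces: 1.5 and 3 per week.

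**Step 1. After the first subject.** Expected further exposures within w days: m = rate × w/7. Chance of at least one: 1 − exp(−m).

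| Rate per week | m, w = 5 | Chance, w = 5 | m, w = 3 | Chance, w = 3 |
|---|---|---|---|---|
| 0.23 | 0.16 | 15% | 0.10 | 9% |
| 1.5 | 1.07 | 66% | 0.64 | 47% |
| 3 | 2.14 | 88% | 1.29 | 72% |

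**Step 2. Over all five gaps, at the slowest pace.** Chance that at least one gap is shorter than w: 1 − (1 − p)^5.
- w = 5 days: p = 0.152, so 1 − 0.848^5 = 0.56.
- w = 3 days: p = 0.094, so 1 − 0.906^5 = 0.39.

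**Step 3. The same test for the existing hold.** The longest window is 6 hours, or 0.25 day. The chance that a given gap is shorter than that is 0.008 at the slowest pace, 0.07 at 2 per week and 0.13 at 4 per week. The trigger information will therefore usually exist before the next exposure. The pre-discharge information may not.

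**Step 4. Cost of waiting.** Five waits of at most 5 days come to 25 days. If patients inside the window are passed over, the expected duration with rate r per day is 1/r + 5 × (5 + 1/r) + 5, that is 6/r + 30 days, the last 5 days being the final subject's stay.
- 3 per week: 14 + 30 = 44 days.
- 1 per week: 42 + 30 = 72 days.
- 6 in 6 months (182.6 days): 182.6 + 30 = about 213 days. Without the hold this would be 182.6 + 5 = about 188 days.

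**The case against.** A reader might infer that subjects are exposed before any safety data exist on the previous one. The protocol does not support that. There is an echocardiogram after separation from bypass; D(1) has the team monitor labs, ECGs and echocardiograms; E(8) describes close post-surgical monitoring, which could prompt an earlier echocardiogram; and the hold triggers are readable within hours. Step 3 bears this out.

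A reader might also call the E(6) list the only brake. It is not. SAEs go to the DSMB chair under E(7), and E(3) counts prolonged hospitalization and important medical events as serious. The third trigger also covers ventricular dysfunction when the stated pressor support is needed. That leaves a narrower gap: myocarditis, or dysfunction short of that support, arising after the operating room.

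Nor can D(6) be read as forecasting several exposures a week. It speaks of eligibility. Enrollment also needs an isolated secundum defect, consent by both parents or by an adult participant, and no exclusion, and section K has one operator do all dye administration and imaging. At 3 per week the study would end in about two weeks. The 88% is therefore an assumed upper scenario, and random arrivals are a rough model for elective surgery. Against this, 6 months is an outer limit rather than a planned pace.

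Prior experience is also more than animal work: section C reports intravenous fluorescein in humans without serious reactions, and the dye here is diluted and washed off. That evidence concerns a different route and does not cover dye with probe contact on the arrested heart.

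Finally, an event-driven hold is a legitimate choice, and section G leaves detailed procedures to a manual of operations that is not shown. That stands as a reason for moderate weight. Whether one subject's result must be known before the next is exposed is nonetheless a safety rule that belongs in the protocol.

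**Conclusion.** The point holds in a limited form. The protocol states nothing false and has a real between-subject rule. That rule does not reach late myocarditis, or ventricular dysfunction without the stated pressor support, although E(6) singles out both outcomes. No text ties the next exposure to the echocardiogram on which they may first appear, and a hold on enrollment does not clearly cover a subject who has already consented.

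The size depends on an exposure rate that the protocol does not give. With random arrivals and a 5-day wait, the chance of at least one further exposure before the first subject's pre-discharge tests runs from 15% at the slowest pace to 88% at an assumed 3 per week. Even at the slowest pace, the chance that some gap among the five is under 5 days is about 56% (39% for 3 days). It does not follow that most of the six would be exposed before a problem was known: expected further exposures in the first window are 0.16 at the slowest pace and reach about 2 only at the fastest rate shown. This is a worthwhile, inexpensive improvement and not a fatal flaw.

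**What to change.** State in D(1) or D(6), and in E(6), that:
- no subject receives study dye or imaging until the previous subject's pre-discharge ECG and trans-thoracic echocardiogram have been read and logged by the study team;
- a finding of myocarditis or ventricular dysfunction on those tests goes to the existing DSMB review before the next exposure;
- both conditions apply to exposure, so that subjects who have consented but not yet had surgery are covered.

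Surgery for a patient whose date falls inside the window goes ahead as usual, without study procedures.

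Both tests are already standard of care, so the change is to wording only. It costs at most five waits of about 5 days (about 25 days in total) and an occasional eligible patient passed over. At one or more enrolled per week the study still fits well within 6 months (about 72 days or less). If accrual is as slow as 6 in 6 months it could overrun, to about 213 days in expectation, and the D(6) timeline should then allow for it.
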